9.4.5 BASELINE DESCRIPTIVE STATISTICS

Not Applicable

9.4.6 PLANNED INTERIM ANALYSES

Not Applicable

9.4.7 SUB-GROUP ANALYSES

We will perform two prespecified secondary analyses, stratifying by **biological sex** and age group (18-44, 45-65, over 65). Effectiveness may differ in these populations because Hug et al. found that 60.3% of preventable plus potential ADEs occur among women while 77.6% occur among adults age 65+.⁶¹

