5 STUDY POPULATION

5.1 INCLUSION CRITERIA

Study Nursing Units:

The study will include 34 acute care areas within Cedars-Sinai medical Center, which are grouped together into 20 nursing units by virtue of sharing the same nursing unit manager (**Table**). To facilitate blocked randomization, we grouped similar nursing units together into 5 blocks with four nursing units per block. The four nursing units within each block are as similar as possible (e.g., medical units are grouped together, ICUs are grouped together, etc.).

Table: Study Nursing Units, Patient Populations, Type, Size, & Allocation to Blocks						
	Unit Areas	Typical Patient Population	Type	Nurses	Pt-Days*	
Block 1: Larger medical floor units						
A	4SE, 4SW	Adult oncology	Floor	118	22,322	
B	5NE, 5NW	Cardiology	Floor	116	21,534	
C	5SE, 5SW	Adult medicine, gastroenterology	Floor	103	22,025	
D	7SE, 7SW	Adult medicine	Floor	92	22,025	
Block 2: Smaller medical floor units and emergency department						
A	6SE, 6SW	Congestive heart failure	Floor	104	18,552	
B	ED	Emergency department (ED)	ED	167	19,108	
C	3-SCCT	Medicine, congestive heart failure	Floor	50	10,188	
D	3NW	Short stay medical	Floor	41	2,437	
Block 3: Surgical floor units						
A	6NE, 6NW 6ICU	Kidney & liver transplant, cardiac surgery, Post cardiac-catheterization recovery	Floor, ICU	122	21,493	
B	7NE, 7NW	Med/surg orthopedics	Floor	106	20,901	
C	8SE, 8SW	Med/Surg bariatrics, GI surgery	Floor	100	15,230	
D	8NE, 8NW	Neurosurgery, Med/surg spine	Floor	78	15,230	
Block 4: Adult intensive care units						
A	4N-SCCT, 6-SCCT	Cardiac ICU, Cardiothoracic surgery ICU	ICU	130	10,711	
B	5-SCCT	Surgical and trauma ICU	ICU	91	6,381	
C	7-SCCT	Respiratory/medical ICU	ICU	69	7,085	
D	8-SCCT, 4NW	Neurosurgical ICU, Adult stroke/medicine	ICU, Floor	124	17,424	
Block 5.1: Obstetric and postpartum units						
A	3NE	Maternal-fetal care (obstetrics)	Floor	123	14,486	
B	3SE, 3SW	Post-partum	Floor	115	13,476	
Block 5.2: Pediatric units						
C	4S-SCCT, 4NE	Pediatric and congenital cardiac ICU, Pediatrics	ICU, Floor	44	3,903	
D	4NICU	Neonatal ICU	ICU	87	9,959	
*Patient-days of care on nursing unit per year.				Total	1980	294,470

Nurses:

- Aims 1 & 3 (SAFE Loop Incident Reports and Medical Record Review): All 1,980 nurses on the nursing units will be eligible to participate in the SAFE Loop and therefore participate in Aims 1 and 3.

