- Aim 2 (Survey): Nurses will be eligible for survey administration if they worked >50% time on one study nursing unit during a 6-month study period; this will ensure adequate exposure to the study conditions and the opportunity to complete baseline and follow-up surveys. About 1,980 nurses will be eligible.
- Qualitative analysis of implementation: Nurse unit managers and nurses will be eligible for the qualitative interview if they worked at least 50% time on the study nursing units for the entire duration of a SAFE Loop implementation period. (We will enroll 32 participants out of a pool of approximately 800 eligible nurses.)

Patients:

Cedars-Sinai has a total of 294,470 patient-days of care in eligible nursing units per year. Patients located in experimental and control group nursing units will be eligible for participation. If patients transfer between nursing units during the study, analyses will allocate each day of the hospitalization to the unit where the patient was that day. For the review of medical records under Aim 3, we will randomly select 1,520 patients hospitalized during the baseline and follow-on periods.

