Non-intercepted (NCC MERP C-D)	A medication error in which the patient received the medication but did not to experience harm.	A patient with a known allergy to an antibiotic receives the drug anyway but does not develop a rash.

*An injury is an unintended consequence of care that negatively affects a patient's health and/or quality of life. † A medication error is an error anywhere in the process of drug ordering, dispensing, administration, and monitoring.

Descriptive Measures: We will characterize event severity/harm (NCC MERP categories), medication class (e.g., cardiovascular, diabetes, etc.), and route of administration (intravenous, oral, etc.). We will classify any errors by stage in drug therapy (ordering, dispensing, administering, monitoring), profession(s) involved (physician, pharmacist, nurse, other), and error types (allergy, drug-disease interaction, drug-drug interaction, drug-lab interaction, duplicate therapy, therapeutic omission, concentration, duration, route/dosage form, dose/frequency/rate, wrong medication, wrong patient, wrong timing, incomplete order).^{5,6,38,61} We will assess which events are Target Medication Events used by Group 1 and 3 nursing units (yes, no; and which unit).

B. Data Collection: The nursing units will implement mitigation plans designed to prevent Target Medication Events toward the end of the SAFE Loop implementation (Section 2B), which means that medication events will not start to fall until after that. Accordingly, we will monitor medication events during a baseline period, the implementation period, and 6-month follow-on period after implementation (Section 3A). To identify medication events, we will randomly sample 1,520 hospitalizations divided equally between the four study groups and the baseline and follow-on periods. (We will exclude the emergency department from Aim 3).

To detect medication events, we will employ the widely accepted Trigger Tool Method by Institute for Healthcare Improvement. It involves two stages: (1) nurses systematically screen medical records for “triggers” (clues that an event occurred) and write synopses of possible events, and (2) physicians review synopses to confirm and classify them. Many studies have used these methods, including studies by Dr. **[name]**.^{5,6,38,61-64}

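### The sex and age subgroup analyses are stratified without any interaction term, so they do not test whether effectiveness differs; the age bands also leave out patients under 18

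*Combined protocol and SAP*

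**What the plan says.** Section 9.4.7 (Sub-Group Analyses) opens with "We will perform two prespecified secondary analyses, stratifying by" biological sex and "age group (18-44, 45-65, over 65". Its reason is "Effectiveness may differ in these populations because" a cited study found uneven shares of preventable plus potential adverse drug events: 60.3% in women, and for age, "77.6% occur among adults age 65" and above. The section names no model term, test or outcome. The rationale concerns medication events, so I read it mainly as an Aim 3 analysis.

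Section 9.4.2 makes the arm-by-period interaction the main hypothesis. It adds a three-way test of arm, period and implementation step, and splits results by step only if that test is significant. Aim 3 follows the same approach. Neither sex nor age appears in any interaction.

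The unit table in section 5.1 lists "Block 5.2: Pediatric units": one unit described as "Pediatric and congenital cardiac ICU, Pediatrics" and a neonatal ICU. Both are among the 20 randomised units. Sections 5.1 and 5.2 set no patient age limit, and the only unit removed from Aim 3 is in section 8.1: "We will exclude the emergency department from Aim 3".

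**The concern.** The stated question is effect modification, and a set of stratum-specific results does not answer it. Two strata can share the same true effect and still differ in significance through noise alone, which invites the claim that the SAFE Loop works in one group only. The plan uses the right device for implementation step but not for sex or age.

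Secondly, the bands begin at 18 in a trial that randomises a neonatal and a paediatric unit, and no sentence says that the age analysis is for adults only. An analyst could add a band, merge minors into the youngest band, or drop them, and each choice would be consistent with some reading of the text.

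A small third point is that 65-year-olds fall in the middle band, while the cited figure counts them with the oldest group.

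**Working it through.** **1. Reproduce the base.** Patient-days by block, from the section 5.1 table: 87,906 + 50,285 + 72,854 + 41,601 + 41,824 = 294,470. This matches the stated total ("Cedars-Sinai has a total of 294,470 patient-days of care in eligible nursing units per year").

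**2. Volume in the two paediatric units.**
- Block 5.2: 3,903 + 9,959 = 13,862 patient-days per year.
- Share of all units: 13,862 / 294,470 = 4.7%.
- Aim 3 base without the emergency department: 294,470 − 19,108 = 275,362. Share: 13,862 / 275,362 = 5.0%.

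The neonatal unit lies outside every band. For the other unit this is inferred from its name, because the documents give no patient ages. Minors on other units would also fall outside the bands, in numbers that cannot be derived.

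**3. Share of charts.** Section 8.1 gives 1,520 / (4 groups × 2 periods) = 190 charts per group and period, but not how they are spread over units. Assuming an even spread within each group and period:
- A group of five units gives 190 / 5 = 38 per unit. The group that loses the emergency department gives 190 / 4 = 47.5.
- Neither paediatric unit in that group: 2 × 2 × 38 = 152 charts (10.0%).
- One of them in that group: 2 × (47.5 + 38) = 171 charts (11.3%).

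Sampling in proportion to patient-days would bring the share down to roughly 5%. One hospitalisation can also span several units. No single chart figure follows from the plan.

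**4. Could minors be tested as a band?** Section 6.3 assigns the four units of a block to four groups, two per arm. Taking Block 5 as one block, once one paediatric unit is placed, the other takes one of three remaining places, of which one is in the same arm. The probability of sharing an arm is therefore 1/3 (8 of 24 permutations). Otherwise the contrast is essentially one unit against one.

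**5. What separate strata would show.** The plan gives no subgroup power, so this is an illustration. Assume 80% power for the main test at two-sided 5%, the same true effect in every stratum, and equal, independent strata. The standardised main effect is 1.960 + 0.842 = 2.802.
- Two strata: power each = Φ(2.802/√2 − 1.960) = 51%. Chance that exactly one is significant = 2 × 0.508 × 0.492 = 50%.
- Three strata: power each = Φ(2.802/√3 − 1.960) = 37%. Chance of mixed results = 1 − 0.366³ − 0.634³ = 70%.

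**6. Power of the interaction test.** With two equal, independent strata, the difference between stratum estimates has twice the standard error of the overall estimate. For an interaction as large as the main effect, power = Φ(2.802/2 − 1.960) = Φ(−0.559) = 29%. Unequal strata would lower this. Unit-level variation shared by the strata would make their results positively correlated, which raises the power and reduces the chance of mixed results.

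**The case against.** The lower limit of 18 is printed in section 9.4.7 and the rationale speaks of adults, so an adults-only age analysis is a legitimate choice visible on the page. A reader might infer that two units are silently lost from the trial. The documents do not support that: the main analyses and the sex analysis keep both units, and the complete loss of the paediatric and cardiac unit even from the age analysis is inferred from its name. A reader might also put the loss at 10% of charts, but that needs an even spread over units which the plan does not state.

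The text says only that results will be stratified. It does not say that p-values will be compared across strata, and the handling of implementation step shows that the authors know the interaction approach. The harm is therefore a risk left open, not a stated intention. The cut at 65 moves a single year of age, so it would be too much to say that the bands contradict their rationale.

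Finally, the recommended test is weak, and adding an under-18 band would create a comparison resting mainly on two units. Both points stand and shape the fix.

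What survives is that no sentence confines the age analysis to adults, and that no sex or age interaction is specified although a difference in effectiveness is the stated reason for looking.

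**Conclusion.** The concern holds as a minor improvement to a secondary analysis. The main part is the missing interaction: as written, section 9.4.7 cannot answer its own question, and under the assumptions of step 5 mixed significance across strata would be common (50% with two strata, 70% with three) even with identical true effects.

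The uncovered age range is smaller. It concerns 5.0% of patient-days outside the emergency department, taking the paediatric and cardiac unit as wholly under 18, and only the age analysis. The one-year mismatch at 65 is trivial but easily removed. None of this affects the primary results. The 29%, 50% and 70% figures are illustrations that rest on the stated assumptions, not on inputs from the plan.

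**What to change.** In section 9.4.7:

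- For sex and for age, fit one model per factor that extends the section 9.4.2 model with the arm-by-period-by-subgroup interaction. Report that test, and the subgroup estimates with intervals from the same model, in place of separate stratum tests.
- Label these analyses exploratory and low-powered.
- State that the age analysis is restricted to adults. Summarise patients under 18 descriptively and do not test them as a band.
- Use bands 18-44, 45-64 and 65 or over, which agrees with the cited rationale.
- Name the outcome or outcomes to which the section applies.

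The cost is a few sentences and a little extra analysis. Age and sex are already to be extracted in Aim 3, so no new data are needed. The downside is an interaction test that will often miss a real difference, which the exploratory label makes plain.

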9.4.8 TABULATION OF INDIVIDUAL PARTICIPANT DATA

Not Applicable

9.4.9 EXPLORATORY ANALYSES

Not Applicable

10 SUPPORTING DOCUMENTATION AND OPERATIONAL CONSIDERATIONS

10.1 REGULATORY, ETHICAL, AND STUDY OVERSIGHT CONSIDERATIONS

10.1.1 INFORMED CONSENT PROCESS

10.1.1.1 CONSENT/ASSENT AND OTHER INFORMATIONAL DOCUMENTS PROVIDED TO PARTICIPANTS

We are requesting a waiver of informed consent for implementation of the SAFE Loop intervention (both nurse and patients) and data collection procedures for Aim 1 (incident reports, both nurses and patients), and Aim 3 (adverse medication events, patients).

For nurses participating in Aim 2 (surveys) we are requesting a waiver of consent documentation. As the survey is via REDCap and is not collecting any identifiable information, requiring a signature would be the only link to a subject's identify. An information sheet will be provided with full consent information. Agreeing to complete and submit the survey will indicate their consent to participate.

For nurses participating in the qualitative interviews of implementation, we will provide consent forms describing in detail the study procedures and risks to the participant. Written documentation of informed consent is required prior to starting intervention/administering study intervention. The following consent materials are submitted with this protocol.

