2.3 RISK/BENEFIT ASSESSMENT

2.3.1 KNOWN POTENTIAL RISKS

There are two categories of study subjects who will be affected by SAFE Loop:

1. **Nurses** and nursing unit managers who work in the nursing units, and
2. **Patients** who receive care there.

Table of Study Procedures and Associated Risks for Each Group.

Study Procedure	Risks for Nurses	Risks for Patients
1. Organizational Quality Improvement Intervention: Implementation of SAFE Loop in nursing units	Psychological distress or loss of professional reputation may occur if a nurse is blamed for a medication error after an incident report is submitted. Risks are similar to those in usual nursing practice because nurses already submit incident reports.	Medication error. Risks are unlikely but may occur if the nursing units inadvertently implement changes that worsen rather than improve medication safety, as intended.

	To further mitigate the risks, we will train nurses to emphasize reporting of near misses and no-harm events (which are less likely to result in punitive responses by unit managers) and train unit managers in the “just culture” approach, which emphasizes changing systems of care rather than blaming individual nurses when medication errors occur.	
2a. Research data collection: nursing work schedules, to assess nurse eligibility for survey	Inadvertent disclosure of individually identifiable information on nursing work schedules. This data source does not include sensitive information.	Not applicable.
2b. Research data collection: surveys of nurses on attitudes toward reporting and patient safety culture	Inadvertent disclosure of individually identifiable information on nursing survey. Survey does not involve sensitive information and it is already routinely deployed in this hospital.	Not applicable.
3. Research data collection: analysis of incident reports to assess rate and quality of reports	Inadvertent disclosure of individually identifiable information. This data source includes sensitive information such as errors that nurses may have committed. Data to be extracted will not include individually identifiable information about nurses.	Inadvertent disclosure of protected health information (PHI). Incident reports contain patient identifiers and PHI. Data to be extracted will not contain patient identifiers aside from randomly assigned study identification numbers to facilitate linkage to other datasets.

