Power calculations are the same for both composite outcome measures. The baseline percentages of positive responses are 75% (H2.1) and 72% (H2.2). We assume 85% of 1980 nurses will be eligible and a 60% response rate (50.5 responses per nursing unit per deployment). We also assume a discrete uniform distribution for each composite measure with only four possible values (0%, 33%, 66%, 100%) per nurse because each measure contains 3 items. Therefore, we assume standard deviation (SD) equal to 37%, and a between-cluster coefficient of variation of 0.65 as recommended by Campbell and Walters.² The **Table** presents the minimum detectable difference in the percentage of positive responses as a function of the intra-cluster correlation (ICC) and presence of implementation trend, using a two-sided t-test for Normal means with 80% power at 5% significance level. Based on prior studies, a meaningful difference in the percentage of positive responses is 8.6 percentage points (pp).³ Missing data patterns will be examined using the method proposed by Little⁴ if the data is found to be not missing at completely random, missing values will be imputed with values drawn from fully conditional specifications using the multivariate imputation by chained equations (MICE) algorithm,^{5,6} with the number of imputed datasets chosen such that the maximum loss of efficiency of 5%.⁷ The plausibility of imputed values will be checked by corresponding diagnostics. The outlined statistical analysis will be performed for each imputed dataset and results will be pooled. All hypotheses will be two-sided at 5% significance level. Calculations will be performed using R-package, version 3.5.3.

Implementation trend	Intra-cluster Correlation			
	0.01	0.05	0.10	0.20
Yes	10pp*	11pp	12pp	13pp
No	7pp	8pp	10pp	11pp

¹ [name] TK, Bell DS, Paddock SM, Hilborne LH. Contributing factors identified by hospital incident report narratives. Qual Saf Health Care. Oct 2008;17(5):368-372.

² Campbell MJ, Walters SJ. How to design, analyse and report cluster randomised trials in medicine and health related research. John Wiley & Sons; 2014.

³ Campione J, Famolaro T. Promising Practices for Improving Hospital Patient Safety Culture. Jt Comm J Qual Patient Saf. Jan 2018;44(1):23-32.

⁴ Little RJ. A test of missing completely at random for multivariate data with missing values. Journal of the American Statistical Association. 1988;83(404):1198-1202.

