Assessment of Survey Measurement Properties: To evaluate the two selected composite measures' internal consistency, we will calculate Cronbach's α using data from baseline survey. To assess construct validity and convergent validity, respectively, we will evaluate associations (Pearson correlation coefficients) between scores on the composite measures and: (1) the full Hospital SOPS, and (2) incident reporting rates at the nursing unit level. To assess responsiveness, we will compare scores from baseline and follow-up surveys among nurses in the SAFE Loop arm (paired t-tests). If the composite measures do not demonstrate good internal consistency, construct, and convergent validity, we will use the full Hospital SOPS.

Statistical Analyses: We will compare changes over time between study arms for Feedback and Communication About Error and Frequency of Events Reported. Multivariable Normal regression models will be fitted for both endpoints and we will test hypotheses similarly to Aim 1. We will adjust for nurse characteristics from the AHRQ survey: years working in this hospital, years worked in current nursing unit, and hours worked per week. We will perform subgroup analyses by years of experience in current profession, because experience has been associated with medication error rates.⁵⁹

Aim 3 Analyses:

Descriptive Analysis: We will calculate rates of preventable ADEs and potential ADEs per 1,000 patient-days, both overall and for the Target Medication Events for the Group 1 and 3 nursing units. We will describe the severity of the events, medication classes, errors, clinicians involved, and stages in drug therapy.

Statistical Analysis: We will compare changes over time between study arms for rates of (a) Target Medication Events per 1000 patient-days and (b) harmful Target Medication Events per 1000 patient-days. Multivariable Poisson models will be fitted with response variable as the number of (a) target medication events and (b) harmful medication events, with offset the length of stay divided by 1000

days. We will test hypotheses similarly to under Aim 1. Model covariates will include patient demographics, biological sex, Elixhauser comorbidity index, and insurance payer.

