Protecting Data from Disclosure: The study team will develop a detailed data safeguarding plan and submit it to the Cedars-Sinai Institutional Review Board and the Data and Safety Monitor and DSMB, if applicable. In brief, all data will be stored on secure, encrypted, password protected servers in locked facilities at Cedars-Sinai. Data transmission will be via secure, encrypted, password protected electronic interfaces. REDCap is a 21 CFR Part 11-compliant web-based database system. Only HIPAA-compliant Limited Datasets will be shared with the Analytical Team (containing dates and study identification numbers).

Details on Data Management by Study Procedure:

Data sources will include nurses' work schedules, surveys of nurses, incident reports, medical records, and qualitative interviews (audiorecordings and transcripts).

Work Schedules, Surveys, and Interviews with Nurses: The work schedules, surveys, and interviews with nurses will be individually identifiable (names, email addresses, possibly dates of birth) but will not contain sensitive information. To determine which nurses are eligible for the survey and interview procedures, we will obtain nurses' work schedules to ascertain how often the nurses work on a particular study nursing unit during the study waves of implementation and whether the nurses worked on the units for an entire study wave. If multiple nurses have the same name, we will use dates of birth and email addresses to distinguish them. We will distribute the survey via Research Electronic Data Capture system (REDCap).

Analysis of Incident Reports: The incident reports themselves constitute sensitive information for nurses and protected health information for patients. The data elements extracted from incident reports will not include individually identifiable information about nurses, but will include protected health information on patients and meet the definition of Limited Datasets under HIPAA. Data elements will pertain to the quality of incident reports and include incident dates and patient study identification numbers.

The analysts will obtain standard certifications in human subjects' protections and be trained to apply study instruments, use the electronic data collection interface, and adhere to study data protection procedures. Analysts will record the extracted data elements in a specially developed data collection interface in REDCap. Data extraction will be conducted by duplicate reviewers and then reconciled to

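### The protocol calls the nurse survey both unlinkable and individually identifiable; run unlinked, the planned paired responsiveness check cannot be computed and the Aim 2 model must ignore repeat responders

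*Combined protocol and SAP*

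**What the plan says.** The protocol describes the survey's identifiability in several places, and they differ.

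- **Section 10.1.1.1 (consent).** The request to waive consent documentation rests on the survey having no tie to the nurse: "As the survey is via REDCap and is not collecting any identifiable information, requiring a signature would be the only link to a subject's identify".
- **Section 10.1.9.1 (data management).** "The work schedules, surveys, and interviews with nurses will be individually identifiable (names, email addresses, possibly dates of birth").
- **Section 2.3.1 (risk table, row 2b).** A listed risk to nurses is "Inadvertent disclosure of individually identifiable information on nursing survey".
- **Section 9.4.2 (survey measurement properties).** "To assess responsiveness, we will compare scores from baseline and follow-up surveys among nurses in the SAFE Loop arm (paired t-tests").
- **Section 5.1 (Aim 2 eligibility).** The rule on working time is justified because "this will ensure adequate exposure to the study conditions and the opportunity to complete baseline and follow-up surveys". Section 8.1 likewise has each eligible nurse surveyed twice.
- **Section 10.1.3 (confidentiality).** A general rule gives participants and their research data a unique study number. It does not mention the survey.
- **Section 10.1.1.2 (consent procedures).** The survey's electronic consent is described together with a form that is signed before any study procedure, although 10.1.1.1 asks to waive that documentation.

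Section 8.1 says the survey goes out as a REDCap weblink in an email, without saying whether the link is individual or generic. For the main Aim 2 analysis, 9.4.2 specifies Normal regression with hypotheses tested as in Aim 1. That means an arm-by-period interaction with random effects for nursing units. No nurse-level term is mentioned.

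**The concern.** A paired test needs each nurse's baseline form matched to her follow-up form. If a signature would be the only link to identity and the signature is waived, no match is possible. The choice has to be made before the baseline deployment, because unlinked forms cannot be matched afterwards.

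Two things are at stake. First, a specified analysis, the responsiveness check, could not be carried out. Second, many nurses may answer both times, and their two answers will be correlated. Without a nurse identifier the Aim 2 model cannot represent that correlation, so its standard error for the change does not reflect the repeat responders.

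**Working it through.** **Step 1. Can the statements be reconciled?** No identifiable data with a signature as the only link (10.1.1.1) is incompatible with individually identifiable surveys (10.1.9.1, and by implication 2.3.1). It is also incompatible with paired t-tests (9.4.2), which need some person-level key even if no name is stored. A coded survey would satisfy 9.4.2 without names, and the study-number rule in 10.1.3 points that way. But no section says the survey carries a code across both deployments, and the wording in 10.1.1.1 excludes one.

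**Step 2. The plan's own inputs (9.2, Aim 2).**

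- Responses per unit per deployment: 1980 × 0.85 × 0.60 / 20 = 50.49 (plan: 50.5).
- SD of a discrete uniform on 0, 33, 66, 100: 37.2 (plan: 37).
- SAFE Loop responses per deployment: 10 × 50.49 = about 505.

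**Step 3. The responsiveness check.** Clustering is ignored, and the within-nurse correlation r is assumed because the documents give none. Unpaired SE of the change = 37 × √(2/505) = 2.33 percentage points (pp). Paired SE = 37 × √(2(1 − r)/number of pairs):

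| r (assumed) | 505 pairs (all linked) | 303 pairs (assumed 60% answer twice) |
|---|---|---|
| 0.3 | 1.95 pp | 2.52 pp |
| 0.5 | 1.65 pp | 2.13 pp |
| 0.7 | 1.28 pp | 1.65 pp |

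Pairing is not always more precise: with 303 pairs and r = 0.3 it is worse than the unpaired comparison. But without a link neither the pairs nor r can be obtained, so the test as written has no data to run on.

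**Step 4. The Aim 2 model.** Let q be the share of respondents who answer both times, m the responses per unit per deployment, and σ² the nurse-level variance. The nurse-level variance of the baseline-to-follow-up difference in a unit mean is (2σ²/m)(1 − qr). A model that treats all forms as independent given the unit uses 2σ²/m. Its nurse-level SE is therefore too large by the factor 1/√(1 − qr):

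| q (assumed) | r (assumed) | 1 − qr | SE factor |
|---|---|---|---|
| 0.4 | 0.4 | 0.84 | 1.09 |
| 0.4 | 0.6 | 0.76 | 1.15 |
| 0.7 | 0.4 | 0.72 | 1.18 |
| 0.7 | 0.6 | 0.58 | 1.31 |

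**Step 5. Dilution by unit-by-period variation.** As an illustration, assume an intra-cluster correlation of 0.05, a correlation of 0.8 between a unit's effects in the two periods, and 50.5 responses per unit, and suppose the model carries that variation. In units of total variance, the nurse term is 2 × 0.95/50.5 = 0.0376 and the unit-by-period term is 2 × 0.05 × 0.2 = 0.0200.

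- Overlap ignored: 0.0376 + 0.0200 = 0.0576.
- Overlap counted, 1 − qr = 0.84: 0.0316 + 0.0200 = 0.0516; SE factor √(0.0576/0.0516) = 1.06.
- Overlap counted, 1 − qr = 0.58: 0.0218 + 0.0200 = 0.0418; SE factor √(0.0576/0.0418) = 1.17.

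So 9% to 31% becomes about 6% to 17% under these assumptions. With a between-period correlation of 1 there is no dilution.

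**The case against.** The strongest reply is that little of consequence depends on the link. H2.1 and H2.2 are tested by an arm-by-period interaction with unit random effects, which runs on unlinked responses. The paired t-test is a one-arm check of responsiveness. It is not among the criteria in 9.4.2 (internal consistency, construct and convergent validity) that would trigger a switch to the full survey. Read together, the named staffing lists, the emailed links, the risk table and the study-number rule suggest coded, confidential handling, with 10.1.1.1 as the outlier. All of this stands, except that the outlier is the stated basis of the waiver and nothing else in the protocol overrides it.

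It is also fair to say that (2σ²/m)(1 − qr) is the true variance of the simple difference whether or not forms are linked. Repeat responders' precision is not destroyed; the model merely fails to credit it. The error is on the conservative side. Shifts in who responds are partly handled by adjusting for years in the hospital, years on the unit and weekly hours.

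A reader might infer several stronger points that the documents do not support:

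- *That nurses are told something untrue.* Section 10.1.1.1 is the rationale for a waiver request. The information sheet is not in the documents, so what nurses read is unknown.
- *That the managers running the intervention solicit the responses.* Section 5.5 has study-team leaders visit the units and nursing unit directors send a supportive email. Section 6.1.1 gives implementation to nursing unit managers. The two roles are not equated.
- *That the iPad lottery needs a link to the form.* A separate entry form would do.
- *That planned imputation fails.* Section 9.2 says only that "missing values will be imputed with values drawn from fully conditional specifications". Nothing there plans to fill one wave from a nurse's other wave.

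**Conclusion.** The contradiction is real and needs resolving. Followed as 10.1.1.1 states, the paired responsiveness check cannot be computed, and the Aim 2 model has to treat a nurse who answers twice as two independent people.

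It would be wrong to conclude that H2.1 cannot be tested or that its test is biased by the missing link. The test runs, with a nurse-level SE component about 9% to 31% too large if q is 0.4 to 0.7 and r is 0.4 to 0.6. The upper figure is the extreme corner of that range, and the total SE is inflated less where units vary between periods. Both q and r are assumptions. The conservatism comes from ignoring overlap only; whether a unit random effect captures unit-by-period variation is a separate question.

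**What to change.** State one rule and use it everywhere. Suggested text for 8.1 and 10.1.9.1: *The survey is confidential and coded. Each eligible nurse is assigned a random study ID, carried in her REDCap link and kept for both deployments. The key linking IDs to names is held outside the Analytical Team and outside nursing management.*

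Then:

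1. Align 2.3.1, 10.1.1.1, 10.1.1.2, 10.1.3 and 10.1.9.1 with that rule. Restate the waiver rationale in 10.1.1.1 on the basis of a coded survey, and settle whether a form is signed (10.1.1.2) or its signature waived.
2. In 9.4.2, add a random effect for nurse within unit to the Aim 2 model.

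If the sponsor prefers true anonymity, keep 10.1.1.1, correct 2.3.1 and 10.1.9.1, and replace the paired t-test with an unpaired or unit-level comparison.

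The coded option costs an IRB wording amendment and a survey setting, with no new data collection. Its downside is that some nurses may be less willing to answer a coded survey than an anonymous one.
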